Rationale: Indonesia is an ageing population with increasing life expectancy, but many elderly people experience functional decline leading to physio-cognitive decline syndrome (PCDS), a reversible condition combining physical (slow gait and reduced grip strength) and cognitive decline (without dementia or disability). PCDS increases the risk of frailty syndrome, disability, and reduced quality of life. Structured physical exercise improves the muscle-brain axis and neuroplasticity markers like mature BDNF. Social isolation worsens PCDS; intergenerational interactions (social heterochronic parabiosis, SHP) may improve cognitive and social domains. However, integrated community-based interventions addressing both physical and psychosocial domains remain limited in Indonesia. Sch

Objective: This study aims to evaluate the effectiveness of a structured chair-based exercise program combined with intergenerational activities compared with usual care in improving physical function, cognitive performance, and frailty status among community-dwelling older adults with physio-cognitive decline syndrome.

Study design: This study is a randomized controlled trial with two parallel arms: (1) chair-based exercise followed by intergenerational activities and (2) usual care. The intervention will be conducted over a defined intervention period with baseline and post-intervention assessments.

Setting: This study will be conducted among community-dwelling elderly individuals in programs managed by the School of Medicine and Health Sciences at Atma Jaya Catholic University of Indonesia and the Archdiocese of Jakarta. The study will include remote tele-exercise and nutritional education, as well as in-person intergenerational sessions at orphanages.

Study population: Community-dwelling elderly aged 60-75 years with PCDS, plus healthy cooperative children aged 5-8 years from orphanages for the intervention arm.

Intervention: Both groups receive nutritional education. Participants in the intervention group will receive a structured chair-based exercise program followed by guided intergenerational activities designed to enhance physical capacity, cognitive stimulation, and social engagement. The control group will receive usual care. Intervention group: 12 weeks structured chair-exercise (PEROSI protocol, progressive frequency 1-3x/week, 60 min/session) followed by 4 weeks SHP (8 sessions, 2x/week, 45 min, paired elderly-child activities using AMIR materials). The control group will receive education only.

Main study parameters/endpoints: The primary outcomes include changes in physical performance and cognitive function. Secondary outcomes include changes in frailty status, quality of life, and psychosocial well-being.

Nature and extent of the burden and risks associated with participation, benefit, and group relatedness: Participation in this study involves minimal to low risk. The primary potential risks are related to the structured chair-based exercise, including mild musculoskeletal discomfort, transient fatigue, muscle soreness, dizziness, or shortness of breath, particularly during the initial sessions. These risks are considered low and are commonly associated with light-to-moderate physical activity in older adults. To minimize these risks, all exercise sessions will be conducted under supervision by trained personnel, with prior health screening and continuous monitoring of participants' physical condition.

Intergenerational activities are non-invasive and pose no physical risk; however, minor psychological discomfort, such as temporary feelings of anxiety or social unease, may occur during initial interactions. These activities will be conducted in a supportive and controlled environment to ensure participants' comfort and emotional safety.

The overall burden to participants includes time commitment for attending intervention sessions and undergoing physical, cognitive, and laboratory assessments. Blood sampling for laboratory analysis may cause mild pain, bruising, or discomfort at the puncture site, with no expected long-term adverse effects.

Potential benefits for participants include improvement in physical function, cognitive performance, frailty status, social engagement, and overall quality of life. The anticipated benefits are considered to outweigh the minimal risks associated with study participation.

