5.1 Investigational product/treatment

All participants (both arms) receive standardized nutritional education as a base intervention:

- Two personalized nutritional consultations via Zoom tele-conference with a certified dietitian (week 1 and week 11), focusing on balanced nutrition tailored to elderly needs.
- Five educational e-flyers on nutrition, physical activity recommendations for the elderly, and related topics (sent via mobile device at weeks 3, 5, 7, 13, and 15).

Intervention group (n=50 elderly + 50 children): In addition to nutritional education, participants receive a sequential multimodal intervention:

1. Structured physical exercise (weeks 1–12):

- Chair-exercise using the Indonesian Osteoporosis Association (PEROSI) protocol, adapted for tele-exercise.
- Sessions: 60 minutes duration, consisting of 10 min warm-up (light aerobic + flexibility), 30 min core (moderate aerobic, strength, balance), 5–10 min cool-down (light aerobic + stretching).
- Frequency progression: 1 session/week (weeks 1–2), 2 sessions/week (weeks 3–6), 3 sessions/week (weeks 7–12).
- Delivery: Online (tele-exercise) supervised by 1 certified PEROSI instructor and assisted by 1 research team member.
- Safety: Pre-session physical condition check; exercise termination based on Borg scale and American College of Sport Medicine (ACSM) guidelines for the elderly.

2. Social Heterochronic Parabiosis (SHP)-based intergenerational intervention (weeks 13–16):

- Group-based direct interaction: Each elderly participant paired 1:1 with one child participant (aged 5–8 years).

- Sessions: 8 total (2 sessions/week, 45 minutes each) conducted in-person at selected orphanages.
- Content: Educational and interactive activities using “Ayo Minum Air” (AMIR) materials from Indonesian Hydration Working Group (comic reading, simple gymnastics demonstration, educational games promoting hydration and healthy lifestyle).
- Organization: Elderly divided into 5 groups (10 elderly each); scheduled visits with research team accompaniment; facilities prepared for conducive interaction (seating, materials, spacing).
- Preparation: Training of Trainers (ToT) for elderly participants and research team during weeks 11–12 (3 sessions, 30 min each, outside exercise schedule).

Control Group

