6. INVESTIGATIONAL PRODUCT

6.1 Name and description of investigational product

This is a non-pharmacological behavioral intervention study. There is no investigational medicinal product or device. The investigational interventions are:

- Structured physical exercise: Chair-based osteoporosis prevention exercise protocol developed by the Indonesian Osteoporosis Association (PEROSI).
- Social heterochronic parabiosis (SHP)-based intergenerational intervention: Direct interactive activities between elderly participants and children using educational materials from the “Ayo Minum Air” (AMIR) program of the Indonesian Hydration Working Group (IHWG), including illustrated comics, simple gymnastics videos, and hydration-focused educational games.

Both interventions are combined sequentially with standard nutritional education (tele-conferences and e-flyers).

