7.3.7 Intervention-specific procedures

- Nutritional education (both groups):
 - Tele-conference consultations (Zoom): Personalized meal planning by dietitian.
 - E-fliers: Digital delivery with confirmation of receipt.
- Structured exercise (intervention group):
 - Pre-session screening: Symptom query, vital signs if needed.

- Session monitoring: Borg Rating of Perceived Exertion scale; termination if excessive dyspnea, pain, dizziness, or hemodynamic changes.
- Intergenerational activities (intervention group):
 - Pre-session preparation: Facility check (seating, materials, spacing).
 - Session structure: Introduction, AMIR-based activities (comic reading, joint gymnastics, games), reflection.
 - Post-session: Brief feedback from the elderly and children.

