7.3.8 Monitoring and adherence

Adherence and safety are monitored proactively to maximize retention and minimize risks.

- Adherence monitoring:
 - Exercise sessions (intervention arm): Attendance logged by instructor and research assistant; session completion confirmed ($\geq 85\%$ of planned sessions required for per-protocol analysis).
 - Intergenerational activities: Attendance sheets signed by research team and orphanage staff; activity completion checklists.
 - Nutritional education (both arms): Confirmation of tele-conference attendance and e-flyer receipt/viewing (via read receipts or follow-up query).
 - Overall: Monthly telephone counseling (2–3 calls/month) by research team to encourage compliance, address barriers, and reinforce motivation.
- Safety monitoring:
 - During exercise phase: Weekly (Monday) pre-session symptom and condition checks by team/instructor; Borg Rating of Perceived Exertion scale monitored throughout sessions; immediate termination for excessive symptoms (severe dyspnea, palpitations, dizziness, heavy weakness, pre-syncope).
 - Bi-weekly direct evaluations (weeks 4, 6, 8, 10): Remote or in-person query on complaints, with direct supervision during selected sessions.
 - Intergenerational phase: On-site supervision by research team and orphanage staff; post-session brief feedback on comfort/discomfort.
 - General: Participants provided with contact number for immediate reporting; all potential adverse events (fatigue, muscle pain, emotional discomfort, minor injuries) documented, managed, and reported to Ethics Committee if serious.

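### The intergenerational sessions list joint gymnastics, but the plan calls them free of physical risk and gives them no pre-session symptom query or stop rule

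*Combined protocol and SAP*

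**What the plan says.** **Risk statement.** The Summary (burden and risks) says "Intergenerational activities are non-invasive and pose no physical risk" and goes on to mention only minor psychological discomfort. Sections 6.4 and 12.1 follow the same line: strain and falls are listed for the chair exercise, and anxiety or awkwardness for the SHP sessions.

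**Session content.** Section 7.3.7 gives the structure of an SHP session as including "AMIR-based activities (comic reading, joint gymnastics, games), reflection". Section 5.1 describes the same content as "simple gymnastics demonstration, educational games promoting hydration and healthy lifestyle". Section 6.1 describes the materials as "including illustrated comics, simple gymnastics videos, and hydration-focused educational games".

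**Safety steps.** In section 7.3.7 the step before an exercise session is "Pre-session screening: Symptom query, vital signs if needed". The step before an SHP session is "Pre-session preparation: Facility check (seating, materials, spacing". The stopping rule in section 7.3.8, "immediate termination for excessive symptoms (severe dyspnea, palpitations, dizziness, heavy weakness, pre-syncope", stands under the exercise phase. For the SHP phase, section 7.3.8 provides supervision by research and orphanage staff and brief feedback on comfort afterwards.

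**Participants.** Section 4.2 requires gait speed below 1.0 m/s and/or grip strength below 28 kg (men) or 18 kg (women).

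**The concern.** The plan accepts a small risk of strain or falls when these participants exercise on a chair under supervision, and it writes checks to match. It then lists gymnastics in a second set of sessions, held in person and paired with children aged 5 to 8, and says that no physical risk exists. If the older adults take part in the gymnastics, whether someone who arrives dizzy or breathless joins in is left to the judgement of whoever is present. Feedback after the session cannot prevent that. The absolute wording also bears on the risks explained at consent under section 10.1.

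**Working it through.** **1. The two session types side by side**

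| | Exercise (weeks 1–12) | SHP (weeks 13–16) |
|---|---|---|
| Before | Condition check (5.1); symptom query, vital signs if needed (7.3.7) | Facility check (7.3.7) |
| During | Borg scale and termination criteria (5.1, 7.3.7, 7.3.8) | Supervision on site (7.3.8) |
| After | Direct evaluations in weeks 4, 6, 8 and 10 (7.3.8) | Feedback on comfort (7.3.7, 7.3.8), counted in 8.1.1 as a way of eliciting adverse events |
| Risks named (6.4, 12.1) | Fatigue, soreness, strain, falls | Psychological only |
| Mitigation (12.2) | Progression, supervision, termination guidance | Preparatory training, supervision |

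Two cells differ in substance: SHP has no query about symptoms before the session and no rule for stopping.

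**2. Do the older adults perform the gymnastics?** Section 7.3.7 says it is joint, section 5.1 speaks of a demonstration and section 6.1 of videos. The preparation in section 5.1, "Training of Trainers (ToT) for elderly participants and research team", would fit older adults showing the movements to the children, but does not say so. The text leaves the question open.

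**3. Number of sessions concerned** (frequencies from section 5.1)

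- Exercise: 2×1 + 4×2 + 6×3 = 28
- SHP: 8
- Share: 8 / (28 + 8) = 8/36 = 22.2%

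The minutes of gymnastics per session are not stated, so this cannot be turned into exposure or risk.

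**4. Secondary check: two missed SHP sessions**

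- Section 7.5.1: 6/8 = 75%, below 85%, and two absences meet the other limb as well, so the participant is a drop-out. One absence, 7/8 = 87.5%, is allowed. Section 9 excludes drop-outs from the primary analysis.
- Section 7.5, non-adherence rule, taking 36 sessions as the denominator (an assumption, as overall completion is not defined): 34/36 = 94.4%, not withdrawn. With 3 exercise sessions also missed, 31/36 = 86.1%, still not withdrawn. With 4, 30/36 = 83.3%, withdrawn.
- Counting the seven education contacts too, 41/43 = 95.3%, which leads to the same conclusion for two SHP absences alone.

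The documents give no absence rate. If absence is p per SHP session and independent (assumptions), the chance of missing two or more of 8 is 1 − (1−p)^8 − 8p(1−p)^7. For p = 2%, 5% and 10% this is 1.0%, 5.7% and 18.7%, or 0.5, 2.9 and 9.3 of 50 participants.

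**The case against.** **SHP sessions are not unmonitored.** A reader might infer that nobody asks about symptoms on the day. The documents do not support that. Feedback on comfort follows each session, section 8.1.1 treats it as a route for eliciting adverse events, and section 7.3.8 adds a contact number and general recording of fatigue, muscle pain and minor injuries. The week-12 visit (section 7.4) measures vital signs, grip, gait speed and frailty shortly before the phase starts. The gap is confined to a query before the session and a stop rule.

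**The gymnastics is simple, and may only be watched.** It comes after 12 weeks of supervised exercise, with staff present. This stands, and it keeps the point modest. If the older adults only watch, the safety gap disappears and the Summary's sentence can remain.

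**The exercise checks may themselves be less than per-session.** Section 7.3.8 describes a weekly Monday check, whereas sections 5.1 and 7.3.7 read as applying to every session. So the other 28 sessions should not be assumed fully covered.

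**On attendance, two stronger readings are tempting.**

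- One is that sections 7.3.8 and 7.5 would keep in the analysis a participant whom section 7.5.1 drops. They do not. The 85% exercise threshold in section 7.3.8 is a necessary condition for per-protocol status and does not override the removal of drop-outs in section 9. Section 7.5 governs withdrawal, not membership of the analysis set.
- The other is that a minor illness can remove an intervention participant but never a control. Section 5.3 withdraws participants for acute illness in either arm with no severity limit, so that contrast is uncertain. Sections 7.5 and 7.5.1 set a higher bar for illness: admission to hospital or inability to continue.

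**Conclusion.** The safety point holds in limited form. The statement that the sessions carry no physical risk does not fit their listed content, and the pre-session query and stop rule are absent from the 8 SHP sessions. The practical weight depends on the older adults performing the gymnastics, which the plan should settle. The 22% counts sessions; a reader should not take it as a share of risk.

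The attendance rules are a secondary observation. Sections 7.5 and 7.5.1 do give different outcomes for a participant who misses two SHP sessions and at most three exercise sessions, and the SHP rule can apply only to the intervention arm. The number affected is unknown, and the range above rests on assumed rates. No loss of power on a primary endpoint follows from the documents: the 42 per group in section 4.5 is the largest requirement across several outcomes and is not tied to a named one.

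**What to change.** 1. In sections 5.1, 6.1 and 7.3.7, state whether the older adults perform the gymnastics or only watch. If they only watch, items 2 and 3 are not needed.
2. If they perform it, add to sections 7.3.7 and 7.3.8: before each SHP session the research team on site asks the existing symptom query, with vital signs if needed; participants with symptoms do only the seated reading and games; the existing section 7.3.8 termination criteria apply to the gymnastics.
3. In the Summary, replace the claim of no physical risk with *low risk of minor strain or falls*, and add that risk to sections 6.4 and 12.1 and to the risks explained under section 10.1.
4. Resolve the differing rules in sections 5.3, 7.5 and 7.5.1 together with the section 3 (intention-to-treat) versus section 9 (per-protocol) conflict over the primary population. Simply exempting illness absences is not a sound repair. Without a minimum dose, someone who attends 1 session and misses 7 through illness would score 1/1 = 100%, and reasons logged by unblinded staff would decide who enters the primary analysis.

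**Cost.** Items 1 to 3 are short text changes in one amendment, with no new staff or visits. At an assumed 1–2 minutes per participant, the query takes 10–20 minutes for a group of 10 if done one by one, best completed before the 45 minutes begin. Participants with symptoms would do less gymnastics that day.

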1. INTRODUCTION AND RATIONALE

Indonesia is a country with an ageing population, with older adults comprising approximately 12% of the total population and a current life expectancy of 72.39 years. The World Health Organization (WHO) has introduced the concept of healthy aging, which emphasizes the importance of maintaining functional ability and intrinsic capacity in older adults to enable them to remain healthy and independent. Impairment of functional ability can lead to disability, which has a greater impact than multimorbidity, underscoring the need for early intervention.

One important early condition in older adults that requires particular attention is physio-cognitive decline syndrome (PCDS), which is defined as the coexistence of physical functional decline (i.e., reduced gait speed or handgrip strength, in the absence of disability) and cognitive decline (without dementia). PCDS increases the risk of frailty and deterioration in quality of life; however, it remains a potentially reversible condition. Multidomain interventions, such as physical and cognitive exercise, have been shown to improve this condition.

One important biomarker of brain neuroplasticity is mature brain-derived neurotrophic factor (mBDNF), which reflects the muscle–brain axis. Social isolation, loneliness, and depression further exacerbate PCDS. Therefore, social interventions such as social heterochronic parabiosis (SHP)—defined as direct interactions between older adults and younger generations, particularly children or adolescents—may represent a promising strategy to improve cognitive function. Intergenerational activities have been shown to enhance mental health, cognitive function, and physical performance in healthy older adults.

To date, no studies have specifically described the model and/or role of SHP-based interventions in improving physical and cognitive decline among older adults with PCDS. This study utilizes educational materials with the potential to facilitate SHP-based interventions in Indonesia, namely the “Ayo Minum Air” (AMIR) campaign developed by the Indonesian Hydration Working Group (IHWG). These educational materials serve as media to facilitate direct interactions between older adults and children (e.g., illustrated comics, exercise videos, and related materials), which are essential components of SHP-based interventions.

This study aims to examine the effects of structured physical exercise followed by SHP-based interventions on frailty syndrome and changes in serum mBDNF levels among older adults with PCDS, as a novel approach integrating physical and social interventions with biomolecular assessment.

2. OBJECTIVES

Primary Objectives

To evaluate the effects of 12 weeks of structured physical exercise (chair-based PEROSI protocol) followed by 4 weeks of social heterochronic parabiosis (SHP)-based intergenerational

intervention on frailty syndrome and serum mature brain-derived neurotrophic factor (mBDNF) levels in community-dwelling elderly with physio-cognitive decline syndrome (PCDS).

Secondary objectives

- To analyze the effects of the combined intervention over 16 weeks on hand grip strength in elderly with PCDS.
- To analyze the effects of the combined intervention over 16 weeks on gait speed in elderly with PCDS.
- To analyze the effects of the combined intervention over 16 weeks on cognitive function as measured by the MoCA-Ina score in the elderly with PCDS.
- To evaluate the effects of the combined intervention over 16 weeks on health-related quality of life in the elderly with PCDS.
- To assess correlations between changes in serum mBDNF levels and changes in MoCA-Ina score, hand grip strength, and gait speed in the elderly with PCDS.

Hypothesis

Elderly people with physio-cognitive decline syndrome (PCDS) who receive 12 weeks of structured physical exercise followed by 4 weeks of social heterochronic parabiosis (SHP)-based intergenerational intervention on top of nutritional education have significantly better frailty syndrome status and higher serum mature brain-derived neurotrophic factor (mBDNF) levels than those receiving nutritional education alone after 16 weeks of intervention, along with greater improvements in hand grip strength, gait speed, cognitive function (MoCA-Ina score), and health-related quality of life.

3. STUDY DESIGN

This is a single-center, randomized, open-label (unblinded), parallel-group controlled clinical trial evaluating the efficacy of a sequential multimodal intervention (structured physical exercise followed by SHP-based intergenerational activities) compared to nutritional education alone in community-dwelling elderly aged 60–75 years with physio-cognitive decline syndrome (PCDS).

The study duration per participant is 16 weeks, consisting of:

- Baseline assessment (week 0)
- Intervention period: 12 weeks of chair-exercise + 4 weeks of intergenerational activities (intervention arm) or continued education (control arm)
- Intermediate assessment (end of week 12)
- Final assessment (end of week 16)

Participants are randomized in a 1:1 ratio into two arms:

- Intervention arm (n=50): Nutritional education + 12 weeks structured chair-based exercise (PEROSI protocol, progressive frequency from 1 to 3 sessions/week, 60 minutes/session, supervised online) followed sequentially by 4 weeks SHP-based intergenerational activities (8 sessions, 2x/week, 45 minutes/session, paired 1:1 elderly-child using AMIR educational materials at selected orphanages).
- Control arm (n=50): Nutritional education only (2 personalized dietitian tele-conferences at weeks 1 and 11; 5 educational e-flyers at weeks 3, 5, 7, 13, and 15).

Randomization is computer-generated using permuted block randomization (block size 4), stratified if necessary, with allocation concealment managed by an independent third party. Blinding of participants and instructors is not feasible due to the nature of the behavioral interventions; however, outcome assessors for laboratory analyses (mBDNF) are blinded to group allocation where possible.

The trial follows intention-to-treat principles with per-protocol sensitivity analysis. Recruitment targets consecutive eligible elderly from community programs under the School of Medicine and Health Sciences at Atma Jaya Catholic University of Indonesia and the Archdiocese of Jakarta. Child participants (aged 5–8 years, n=50) are recruited from cooperating orphanages exclusively for the intervention arm.

